##### **The proportion of participants who did not require rescue ITP therapy after Week 3 (ie, Week 3 to Week 24, 56, and the end of on-treatment period)**

The proportion will be summarized at Week 24, Week 56, and the end of on-treatment period separately for the ITT along with the 95% exact Clopper-Pearson CI.

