## **2 SAMPLE SIZE DETERMINATION**

Approximately 12 participants will be enrolled. Since there is no statistical hypothesis to be tested in this study, the sample size is not determined statistically.

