**Table 2 - Populations for analyses**

Population	Description
Enrolled	All participants from screened population who have been allocated to an intervention regardless of whether the intervention was received or not.
Intent-to-treat (ITT)	All exposed participants.
Safety	All enrolled participants who take at least 1 dose (including partial dose) of study intervention.
Pharmacokinetic (PK)	All enrolled and treated participants (safety population) with at least one post-baseline PK sample.
Pharmacodynamic (PD)	All enrolled and treated participants (safety population) with at least one post-baseline PD sample.
ADA	All enrolled and treated participants (safety population) with at least one post-baseline ADA sample.

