#### *Observation period*

The observation period will be divided into 3 segments:

- The **pre-treatment period (or the screening period)** is defined as the period from the time of the signing of the informed consent form (ICF) to the first IMP administration.
- The **on-treatment period** is defined as the period from the first IMP administration to the last IMP administration +7 days.
- The **post-treatment period** is defined as the period after the on-treatment period.

The **treatment-emergent** (TE) period includes both on-treatment period and post-treatment period.

Analyses of safety will be based on the treatment-emergent period.

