#### **4.4 SECONDARY ENDPOINT(S) ANALYSIS**

Participants will continue to receive BIVV020 until the last participant enrolled has completed 52 weeks of treatment. Week 52 is not a scheduled visit and therefore replaced by Week 56 for secondary endpoint(s) analysis. All available data up to Week 56 during the on-treatment period will be included.

The key secondary endpoints include:

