##### **Time from baseline to first platelet response $\geq 50 \times 10^9/L$ (confirmed by 2 measurements at least 7 days apart) during 56 weeks of treatment**

##### **Time from baseline to first platelet response $\geq 100 \times 10^9/L$ (confirmed by 2 measurements at least 7 days apart) during 56 weeks of treatment**

[figure not shown]
To qualify for the event, both platelet counts have to be  $\geq 50 \times 10^9/L$  (or  $\geq 100 \times 10^9/L$ ) and collected  $\geq 7$  days apart without any platelet count less than the threshold in between. Platelet counts collected at unscheduled visits are included.

Kaplan-Meier estimates will be calculated for time to the first of the two qualifying platelet counts. The 25%, median, 75% time to event along with 95% CI will be presented. The Kaplan-Meier survival curve will be presented.

For participants who do not have a platelet response, their time-to-event will be censored:

- at Week 56 for those treated beyond 56 weeks
- at Week 57 (1 week after Week 56) for those who prematurely discontinued the treatment due to any adverse event (AE) or lack of response before Week 56
- at the time of treatment discontinuation for those who prematurely discontinued the treatment before Week 56 due to reasons other than AE or lack of response.

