### ***Prior or concomitant medications***

All medications will be coded using the World Health Organization-drug dictionary (WHO-DD) using the version currently in effect at Sanofi at the time of database lock.

- Prior medications are those the participant used prior to first IMP intake. Prior medications can be discontinued before first administration or can be ongoing during treatment period.
- Concomitant medications are any interventions received by the participant concomitantly to the IMP during the on-treatment period.
- Post-treatment medications are those the participant took in the period running from the end of the concomitant medications period up to the end of the study.
- A given medication can be classified as a prior medication and/or as a concomitant medication and/or as post-treatment medication. If it cannot be determined whether a given medication was taken prior or concomitantly or post, it will be considered as prior, concomitant, and post-treatment medication.

The prior, concomitant, and post-treatment non-ITP medications will be summarized for the ITT population, by anatomic and therapeutic level. The summaries will be sorted by decreasing frequency of anatomic category (ATC) based on incidence in intervention group. Therapeutic classes are sorted by decreasing frequency within each anatomic class. In case of equal frequency, alphabetical order will be used. Participants will be counted once in each ATC category (anatomic or therapeutic) linked to the medication.

Prior ITP, concomitant non-rescue ITP, and concomitant rescue ITP therapies/medications will be summarized separately by the ATC level 4 chemical class and medication name. All ITP therapies will be listed with rescue ITP therapies flagged.

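### Rescue-free proportion: applied literally, SAP 4.4 counts participants who stop BIVV020 early without on-treatment rescue as rescue-free at Weeks 24 and 56

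*SAP*

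**What the plan says.** The SAP defines the rescue endpoint over three windows ("ie, Week 3 to Week 24, 56, and the end of on-treatment period") and gives each a proportion with an exact Clopper-Pearson interval: "The proportion will be summarized at Week 24, Week 56, and the end of on-treatment period separately for the ITT". Four other provisions determine who falls in the numerator and denominator.

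- SAP 4.4, opening paragraph, on the data used for secondary endpoints: "All available data up to Week 56 during the on-treatment period will be included".
- SAP 4.1, Observation period: the on-treatment period "is defined as the period from the first IMP administration to the last IMP administration +7 days".
- SAP Table 2: the ITT population is "All exposed participants".
- SAP 5.3: "Concomitant medications are any interventions received by the participant concomitantly to the IMP during the on-treatment period". Anything taken later is classed as post-treatment medication.

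Neither SAP 4.4 nor Protocol 9.3.3 says how a participant who stops BIVV020 early is classified for this endpoint. Two other endpoints do have a rule. In Protocol 9.3.2, stopping before Week 3 is non-response for the primary endpoint. In SAP 4.4, participants without a platelet response are censored in the time-to-response analysis "at Week 57 (1 week after Week 56) for those who prematurely discontinued the treatment due to any adverse event" or for lack of response. They therefore stay in the risk set without an event for the whole period.

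**The concern.** Missing follow-up does not act in the same direction on every endpoint. For a response endpoint it tends to count against the drug, because a response has to be observed. For an absence-of-event endpoint it counts in the drug's favour, because a rescue that falls outside the data window is the same as no rescue. The rescue-free proportion is of the second kind, and it is the endpoint without a discontinuation rule.

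The situation is foreseeable. Lack of efficacy is a listed reason for permanent discontinuation (Protocol 7.1.1 and 7.1.4), and Protocol 2.3 reports a 50% clinical response with the earlier C1s inhibitor in ITP, so some non-response should be expected. Under Protocol 7.1.1 a participant who stops may be replaced, but still belongs to the ITT population. What is at stake is whether a figure labelled Week 24 or Week 56 describes freedom from rescue to that week, or only up to whenever each participant stopped.

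**Working it through.** **No plan figure to reproduce.** The SAP gives no power calculation or target for this endpoint: "Since there is no statistical hypothesis to be tested in this study, the sample size is not determined statistically". The check applies the SAP's rules and then illustrates the size.

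**Step 1: evaluable time.** Week 3 is Day 22 (Protocol 1.3) and Week 24 is Day 169 (SAP Table 6), so the window is 169 − 22 + 1 = 148 days. The on-treatment period ends at last dose + 7 days. Evaluable days = max(0, min(last dose + 7, 169) − 22 + 1).

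| Last dose | On-treatment ends | Evaluable days | Share of 148 |
|---|---|---|---|
| Day 1 | Day 8 | 0 | 0% |
| Day 8 | Day 15 | 0 | 0% |
| Day 15 | Day 22 | 1 | 0.7% |
| Day 29 | Day 36 | 15 | 10% |
| Day 85 | Day 92 | 71 | 48% |

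Each of these participants stays in the ITT denominator. With no rescue recorded in the evaluable days, each also enters the rescue-free numerator at Week 24 and Week 56.

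**Step 2: size.** Assumptions, none from the documents except the approximate total: n = 12; 2 participants rescued on treatment after Week 3; d participants who stop early without such rescue, with d from 0 to 4. The 95% limits for x out of n are the 0.025 quantile of Beta(x, n − x + 1) and the 0.975 quantile of Beta(x + 1, n − x).

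| d | SAP applied literally | Stoppers counted as failures, (10 − d)/12 |
|---|---|---|
| 0 | 10/12 = 83.3% (51.6 to 97.9) | 10/12 = 83.3% (51.6 to 97.9) |
| 1 | 10/12 = 83.3% (51.6 to 97.9) | 9/12 = 75.0% (42.8 to 94.5) |
| 2 | 10/12 = 83.3% (51.6 to 97.9) | 8/12 = 66.7% (34.9 to 90.1) |
| 3 | 10/12 = 83.3% (51.6 to 97.9) | 7/12 = 58.3% (27.7 to 84.8) |
| 4 | 10/12 = 83.3% (51.6 to 97.9) | 6/12 = 50.0% (21.1 to 78.9) |

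Each such stopper is worth 1/12 = 8.3 points, and the literal SAP figure does not move with d. The right-hand column is the most adverse reading. If only stoppers who are actually rescued later count as failures, the result lies between the two columns. Dropping stoppers from the denominator gives 9/11 = 81.8% (d = 1) to 6/8 = 75.0% (d = 4), but that is no longer the ITT population.

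**Step 3: can later rescue be counted?** Protocol 7.1.1 asks for 22 weeks (154 days) of follow-up after permanent discontinuation, and Protocol 6.8 requires medication during the study to be recorded. Follow-up reaches Week 24 if the last dose is on Day 169 − 154 = Day 15 or later. Taking Week 56 as Day 56 × 7 + 1 = 393, it reaches Week 56 only if the last dose is on Day 393 − 154 = Day 239 or later. Off-treatment data therefore cover Week 24 for almost everyone who stops after Week 3, but Week 56 only for later stoppers.

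**The case against.** The strongest reply is that the SAP nowhere says early stoppers are successes. That is correct. The classification follows from three stated rules and one missing rule, and a programmer could resolve the silence differently.

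Secondly, the on-treatment window is a planned choice. Protocol 9.3.1 already ends the efficacy period at last dose + 7 days, so the SAP did not introduce it, and an on-treatment summary of rescue is a legitimate description in a single-arm study. This stands, but the SAP has a separate summary for exactly that purpose, to the end of the on-treatment period. Proportions labelled Week 24 and Week 56 suggest a common length of observation that early stoppers do not have.

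Thirdly, the primary-endpoint comparison reaches only so far. A reader might infer that someone who stops at Week 6 would automatically fail the primary endpoint. Protocol 9.3.2 does not say so: after Week 3 it uses the available data. Only stopping before Week 3 gains support from that rule.

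Fourthly, the SAP offers partial safeguards. Section 4.2 reports treatment non-completion with main reasons, and section 5.3 lists all ITP therapies with rescue flagged. With about 12 participants a careful reader could trace each case. That helps interpretation but does not correct the proportion or its interval.

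Finally, counting every stop for an adverse event as a rescue failure would change the endpoint. A participant who stops for an allergic reaction with good platelet counts has not needed rescue. This objection stands and shapes the fix.

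**Conclusion.** The point holds as a missing classification rule whose literal application biases the rescue-free proportion upward. It affects only participants who stop early with no rescue between Week 3 and last dose + 7 days. Anyone rescued on treatment after Week 3 is counted correctly, and rescue on treatment is permitted (Protocol 6.8.1). A reader might therefore infer that all early failures are scored as successes; the documents do not support that.

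The size cannot be fixed from the documents. Under the assumed 12 participants and 2 on-treatment rescues, counting stoppers as failures lowers the estimate from 83.3% to 75.0% with one stopper and to 50.0% with four. The last figure is the far end of an assumed range, not an expectation: Protocol 7.1.1 describes permanent discontinuation as rare, and the intervals overlap widely. The endpoint is secondary and descriptive, so no type I error or sample size is affected. It still deserves correction, because a participant with no evaluable time cannot fail and the plan guards against early stopping elsewhere.

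**What to change.** In SAP 4.4, under the rescue endpoint:

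1. Classify participants who discontinue BIVV020 before Week 3 as not rescue-free, matching the primary-endpoint rule in Protocol 9.3.2.
2. For Week 24 and Week 56, count rescue ITP therapy recorded up to that time point whether or not it falls after last dose + 7 days. Keep the on-treatment result as the separate third summary. State how participants whose follow-up ends before Week 56 are handled and how many there are.
3. Add a Kaplan-Meier time to first rescue, which accommodates unequal follow-up, and a sensitivity analysis counting discontinuation for lack of response as failure, with stops for adverse events shown separately. Print the number of early stoppers beside each proportion.

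Because item 2 departs from the efficacy period in Protocol 9.3.1, record it in SAP Appendix 2, Changes to protocol-planned analyses. The cost is SAP wording, one more derivation with its supporting outputs, and a possibly less favourable figure. No new data collection is needed: discontinuation reasons are already summarised, and the schedule of activities includes medication review through the end-of-study visit.

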##### **Time from baseline to first platelet response $\geq 50 \times 10^9/L$ (confirmed by 2 measurements at least 7 days apart) during 56 weeks of treatment**

##### **Time from baseline to first platelet response $\geq 100 \times 10^9/L$ (confirmed by 2 measurements at least 7 days apart) during 56 weeks of treatment**

[figure not shown]
To qualify for the event, both platelet counts have to be  $\geq 50 \times 10^9/L$  (or  $\geq 100 \times 10^9/L$ ) and collected  $\geq 7$  days apart without any platelet count less than the threshold in between. Platelet counts collected at unscheduled visits are included.

Kaplan-Meier estimates will be calculated for time to the first of the two qualifying platelet counts. The 25%, median, 75% time to event along with 95% CI will be presented. The Kaplan-Meier survival curve will be presented.

For participants who do not have a platelet response, their time-to-event will be censored:

- at Week 56 for those treated beyond 56 weeks
- at Week 57 (1 week after Week 56) for those who prematurely discontinued the treatment due to any adverse event (AE) or lack of response before Week 56
- at the time of treatment discontinuation for those who prematurely discontinued the treatment before Week 56 due to reasons other than AE or lack of response.

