5.1 INCLUSION CRITERIA

Participants are eligible to be included in the study only if all the following criteria apply:

Age

I 01. Male and female participants ≥ 18 years of age at the time of signing the informed consent.

Type of participant and disease characteristics

I 02. Confirmed diagnosis of primary ITP; for participants who previously received sutimlimab in study TDR16218, a response to sutimlimab must have been obtained, as defined by platelet count $\geq 30 \times 10^9/L$ on 2 visits at least 7 days apart.

I 03. For participants who have not previously received sutimlimab: persistent/chronic ITP (ITP lasting for ≥ 6 months) and all the following conditions:

- a) Platelet count $\leq 30 \times 10^9/L$ on 2 occasions at least 5 days apart during the Screening Period;
- b) Lack of an adequate platelet count response (as defined by maintenance of sustained platelet count $\geq 30 \times 10^9/L$ in the absence of bleeding) to at least 2 ITP treatments, 1 of which was a thrombopoietin receptor agonist. Other ITP treatments include: IVIg, anti-D immunoglobulin, corticosteroids, splenectomy, rituximab, cyclophosphamide, azathioprine, danazol, cyclosporin A, mycophenolate mofetil, or fostamatinib.
- c) If receiving weekly thrombopoietin receptor agonist dosing, the last dose must have been administered ≥ 7 days before the first dose of BIVV020. If receiving daily thrombopoietin receptor agonist dosing, the last dose must have been administered ≥ 24 hours before the first dose of BIVV020.
- d) If applicable, concurrent administration of ITP medications (eg, corticosteroids, IVIg, azathioprine, danazol, cyclosporin A, mycophenolate mofetil, or thrombopoietin receptor agonists) is acceptable provided the patient has been on a stable dose for at least 1 month. See [Section 6.8](#) for additional details.
- e) If previously dosed with rituximab, the last dose of rituximab must have been administered at least 12 weeks before the first dose of BIVV020.
- f) If previously dosed with cyclophosphamide, the last dose of cyclophosphamide must have been administered at least 4 weeks before the first dose of BIVV020.

I 04. Documented vaccinations against encapsulated bacterial pathogens (*Neisseria meningitidis*, including serogroup B where available, *Haemophilus influenzae*, and *Streptococcus pneumoniae*) within 5 years of enrollment, or as specified in [Section 8.2.6](#).

Contraception

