6.8 CONCOMITANT THERAPY

Any medication or vaccine (including over the counter or prescription medicines, vitamins, and/or herbal supplements, and rescue medication) that the participant is receiving at the time of enrollment or receives during the study must be recorded along with:

- Reason for use
- Dates of administration including start and end dates
- Dosage information including dose and frequency

Vaccinations such as seasonal influenza vaccines and other recommended vaccines and booster vaccinations are permitted as per local standard of care, investigator discretion, and local labels.

Concurrent administration of ITP medications (corticosteroids, IVIg, azathioprine, danazol, cyclosporine A, mycophenolate mofetil, or thrombopoietin receptor agonists) is acceptable provided the patient has been on a stable dose for at least 1 month. This applies for both new patients and patients who were previously receiving sutimlimab in Study TDR16218.

Corticosteroids, thrombopoietin receptor agonists, and IVIg are permitted, if the following requirements are met:

- A) Corticosteroids: the first dose of BIVV020 may be dosed only ≥ 4 days after a steroid pulse (single dose of >0.5 mg/kg prednisone equivalent or an increase in prednisone equivalent dose from prior levels) for acute ITP treatment
- B) Thrombopoietin receptor agonists: If receiving weekly thrombopoietin receptor agonist dosing, the last dose must have been administered ≥ 7 days before the first dose of BIVV020. If receiving daily thrombopoietin receptor agonist dosing, the last dose must have been administered ≥ 24 hours before the first dose of BIVV020. Thrombopoietin receptor agonists may be restarted by the Investigator if a participant has an insufficient response to BIVV020.
- C) Intravenous Ig (IVIg): the first dose of BIVV020 must be dosed ≥ 1 day after a dose of IVIg. A single dose of IVIg is allowed during the study; additional doses after the first dose must be approved by the Sponsor.

The Medical Monitor should be contacted if there are any questions regarding concomitant or prior therapy.

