## 5.4 APPENDIX 4 DATA HANDLING CONVENTIONS

### Study Day

Study Day is defined as days relative to the date of first IMP administration (ie, D1 as in the protocol). The Study Day of an event is calculated as

- (date of event – date of first IMP administration + 1), if the event is on or after the first IMP administration;
- (date of event – date of first IMP administration), if the event is prior to the first IMP administration.

The date of the first IMP administration is Study Day 1.

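### Time to first platelet response has no rule for participants already at the threshold, or recently given IVIg, a steroid pulse or rescue, so early events need not mark the onset of response to BIVV020

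*SAP*

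**What the plan says.** SAP 4.4 defines the event for each threshold by two counts at or above it, at least 7 "days apart without any platelet count less than the threshold in between". It adds that "Platelet counts collected at unscheduled visits are included" and that "Kaplan-Meier estimates will be calculated for time to the first of the two qualifying platelet counts". The event therefore takes the date of the first count, not the confirming one. The rule and its censoring provisions mention neither prior nor rescue ITP therapy, and no rise from a pre-dose value is required. Protocol 9.3.3 adds no such condition.

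The time origin is called baseline. No date is given for it, but SAP 5.4 says "The date of the first IMP administration is Study Day 1", so Day 1 is the natural reading.

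On pre-dose treatment, Protocol 6.8 says "Corticosteroids, thrombopoietin receptor agonists, and IVIg are permitted, if the following requirements are met". The first dose must come at least "1 day after a dose of IVIg" and at least 4 days after a steroid pulse given for acute ITP. The same section, and inclusion criterion I 03 d, say that concurrent ITP medication "is acceptable provided the patient has been on a stable dose for at least 1 month".

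For naive participants, I 03 a requires two low counts during a screening period of up to 56 days and sets no limit on Day 1. For switchers, I 02 requires a past response to sutimlimab (at least 30 × 10⁹/L on two visits) and sets no upper limit at entry.

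**The concern.** The secondary objective is the time to response to BIVV020. Two kinds of participant can produce an early event that is not onset of such a response:

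- A naive participant treated with IVIg or a steroid pulse between the last low screening count and Day 1, or rescued soon after Day 1, whose raised counts confirm each other.
- A participant, most plausibly a switcher, whose count was already at or above the threshold before the first dose.

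The neighbouring endpoints have some protection. The primary endpoint starts at Week 3 and bars concomitant ITP therapy. The Week 24/56 response rate requires a more than 2-fold rise and bars concomitant ITP therapy while counts are above the threshold. Time to response is the endpoint most exposed to the first days, and it has neither safeguard. Borrowing the wording of the Week 24/56 endpoint would not close the gap: SAP 5.3 defines concomitant by the on-treatment period, so a single dose given before Day 1 is classed as prior.

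At stake are the early part of the curve and the quartiles that SAP 4.4 reports. Once an early event is recorded, that participant's later course no longer affects this curve.

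**Working it through.** The plan states no figure to reproduce, since the sample size is not determined statistically. The check has three parts.

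**1. How long carry-over must last.** Inputs: visit days from the schedule of activities and SAP Table 6 (Days 1, 4, 8, 15); the 7-day confirmation gap from SAP 4.4; the shortest permitted intervals from Protocol 6.8. With IVIg 1 day before Day 1, Day d is d days after IVIg. With a pulse 4 days before Day 1, Day d is d + 3 days after the pulse.

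| First count | Confirming count | Gap (days) | Days after IVIg | Days after pulse | Event dated |
|---|---|---|---|---|---|
| Day 1 post-dose | Day 8 | 7 | 8 | 11 | Day 1 |
| Day 4 | Day 8 | 4 (too short) | – | – | none |
| Day 4 | Day 15 | 11 | 15 | 18 | Day 4 |
| Day 8 | Day 15 | 7 | 15 | 18 | Day 8 |

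A Day 15 visit at the early edge of its ±1 day window shortens 15 and 18 to 14 and 17. The Day 8/Day 15 gap can then fall below 7 days, but Day 4/Day 15 remains at least 9 days apart.

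The Day 1 row has two further requirements. SAP 4.1 places the 0-hour count in baseline, so a 4-hour or unscheduled count is needed; the 4-hour count is read from a schedule table whose extraction may be imperfect. With IVIg only the day before, the count must also rise from the low screening level to the threshold within about a day.

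The documents do not say how long IVIg or a pulse acts. For IVIg the day before Day 1:

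- under about 8 days, no false event;
- 8 to 14 days, only with a Day 1 post-dose or unscheduled count;
- 15 days or more, on the regular schedule.

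**2. Participants already at the threshold.** No assumption about duration is needed. If the last pre-dose count is at or above 50 and the counts through Day 15 stay there, the event is dated Day 4 at the latest, although nothing has changed since before dosing. How many will enter this way is unknown, because I 02 asks for 30 and not 50. The ceiling from switchers alone is 6/12 = 50%.

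**3. Effect on the planned curve.** With no earlier censoring, k such events among n participants raise the cumulative response by k/n. At n = 12, 1/12 = 8.3 points and 3/12 = 25%, which sets the 25% time (taken as the first day the curve reaches 25%).

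An invented example shows the scale. Take 12 participants, with 6 true responders at Days 15, 29, 43, 57, 71 and 85. The 25% time is the third event (Day 43) and the median is the sixth (Day 85). Let some of the other 6 have a carry-over event at Day 4:

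| Carry-over events | 25% time | Median |
|---|---|---|
| 0 | Day 43 | Day 85 |
| 1 | Day 29 | Day 71 |
| 2 | Day 15 | Day 57 |
| 3 | Day 4 | Day 43 |

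**The case against.** The SAP implements the protocol's endpoint as written, and that endpoint carries no therapy condition. The analysis is descriptive, with about 12 participants and no hypothesis test. Questions conditioned on therapy are answered by the primary and Week 24/56 endpoints. SAP 5.3 lists all ITP therapies and SAP 4.3 plots individual platelet profiles, so an early event after IVIg could be spotted by eye. The confirmation rule filters out short-lived effects. The spacing rules in Protocol 6.8 can also be read as additions to the 1-month stable-dose rule; on that reading maintenance IVIg was already in place when the low screening counts were taken.

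Much of this stands. It limits the size of the problem and rules out any claim about error rates. It does not remove the gap. Listings and profiles do not change the curve or its quartiles. The stable-dose reading does not readily cover an acute steroid pulse, and it does not touch switchers or rescue after Day 1.

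A reader might infer that Protocol 6.8 flatly contradicts itself. The text does not force that, but how the allowances fit the stable-dose rule is unclear and the passages must be reconciled.

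**Conclusion.** The point holds in a limited form. As written, the rule can record carry-over, rescue effect or a pre-existing count as a response to BIVV020. Each such event is worth about 8 points on the planned all-participant curve at n = 12, and three set the 25% time. For pre-dose therapy this rests on an effect of about 15 days (IVIg) or 18 days (pulse) on scheduled Day 4, 8 and 15 counts, or about 8 and 11 days with a Day 1 post-dose or unscheduled count. It also assumes that Day 1 is the origin and that the figure not shown in this part of SAP 4.4 adds no condition.

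Stronger readings are tempting but unsupported:

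- *That false events within days are to be expected.* The documents give neither the duration of effect nor the frequency of such dosing, and the Day 1 case needs the extra conditions above.
- *That the participant's true later course is lost.* It still counts in the primary and Week 24/56 endpoints; it is lost only from this curve.
- *That each event is worth more because only naive participants count.* SAP 4.4 plans no naive-only curve.

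**What to change.** In SAP 4.4:

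1. State that a participant whose last pre-dose count is at or above a threshold is left out of the risk set for that threshold and listed separately. Use the last count, because SAP 4.1 defines platelet baseline as an average of pre-dose values, which can hide a late rise. Say explicitly that these participants are removed, not censored; otherwise the Week 56 censoring rule could treat them as non-responders. Present naive participants and switchers separately.
2. Keep the all-counts analysis for everyone else. Add a pre-specified sensitivity curve in which a count cannot qualify within a stated window after IVIg, a steroid pulse or increase, a platelet transfusion or other rescue ITP therapy, including doses before Day 1. The sponsor should justify the window. One option is 28 days, which has no source in the documents and is therefore offered only for sensitivity. Another is to let counts qualify only from Week 3, as in the primary endpoint; this deals with most pre-dose carry-over but not with later rescue.

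The cost is SAP wording and a date check against medication dates that Protocol 6.8 already requires to be recorded. A few participants or early counts drop out, and split curves are coarser (1/6 = 16.7 points per event in a group of 6). In the sensitivity curve a genuine early response may be dated late: with a Week 3 start, no event can be dated before about Day 22, or Day 29 if Day 22 has no scheduled platelet count. No treatment rule changes.
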